In the three groups of intraoperative blood oxygen changes (Table 2), without intubation and without muscle relaxants, the CO₂ content in the body is less than that of muscle relaxants, and there is no possibility of PaCO₂ ≥ 80mmHg. In the postoperative discomfort reaction (Table 3), 1 patient in group 1 and 3 had sore throat, and 1 patient in group 3 had difficulty breathing when he was interviewed in the recovery room. The side effects of postoperative nausea and vomiting (Table 4), each of the first group and the third group had nausea and vomiting. In the vital signs before, during and after the operation (Table 5), the heartbeat of the second group had an upward trend during the operation. In the surgical field of vision (Table 6), one in the first group affected the field of vision due to the appearance of congenital structures, one in the third group had an abnormal vocal cord structure that affected the field of vision, and the second group had no poor surgical field of vision. A questionnaire survey by the chief surgeon (Table 7) showed that the surgeons were satisfied with the surgical satisfaction of the three groups, but the pressure was higher when performing non-intubation and nerve block surgery.

Each group must collect 30 people, to compare the effects of intubation and non-intubation on the surgical field of vision and the changes in blood oxygen during the operation. At present, we have collected data on 29 patients. We anticipate that

needed 61 patient data. In order to achieve the accuracy and legibility of the number of statistical samples. And to explore the safety of laryngoscope microsurgery under non-intubation anesthesia.

B BACKGROUND AND PURPOSE

Importance and research status of this project at home and abroad, and indicate important documents ◦

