During the operation, a pulse oximeter will be used to monitor and record the patient's oxygen saturation. The patient's gender, height, weight, BMI, age, past medical history, ASA classification, type of laryngoscopic surgery, operation time, lesion location, blood loss, and anesthesia records will be kept.

All three groups of patients will use radial artery catheters. In addition, the three groups performed arterial blood gas analysis (including: PaO₂, PaCO₂, pH, HCO₃⁻) at the following times to understand the difference of pCO₂ in different groups and as a secondary result.

The first period to measure those variables is before each set of surgery are follows:

The first group is before tracheal intubation.

The second group was before the administration of muscle relaxants.

The third group is before applying superior laryngeal nerve block bilaterally.

The second period to measure those variables is the end of the operation.

The third period to measure those variables is 15 minutes after entering the recovery room.

All the anesthesia time, operation start time and operation end time of the three groups will be recorded, and the relationship between them will be discussed.

After the operation, the surgeon and the patient will be asked to do a questionnaire survey in order to understand whether the non-intubation anesthesia laryngoscope microsurgery of the self-breathing causes obstruction or other difficulties for the operator, as well as the patient's postoperative recovery, surgical satisfaction and operation After scoring. Finally, the surgeon's score on the degree of surgical completion was taken as the primary outcome.

Conditions for participating in this research project:

- Subjects are between 20-80 years old.
- Patients undergoing laryngoscope microsurgery.

- Anesthesiologists rated ASA as between I and III.

If those who are included have any of the following conditions, you will not be able to participate in this research project:

- Having drug dependence and drinking habits.
- Abnormal heart, liver and kidney function.
- Allergic reactions to narcotic drugs.
- Emergency surgery.
- pregnancy.
- Refuse to participate.

This study will explore the following assumptions:

Ho1: The intraoperative field of vision of the nonintubation group is clearer than that of the intubation group.

Ho2: Non-intubation and no muscle relaxation has less carbon dioxide retention and less hypercapnia.

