Ho3: There is less sore throat in the nonintubation group than in the intubation group.

Ho4: Non-intubation and no muscle relaxation may lead to less postoperative pulmonary complications.

Ho5: In the non-intubation group, no muscle relaxants are more suitable for long-term surgery than those with muscle relaxants.

Statistical analysis (the statistical analysis tool will use IBM SPSS version 20):

- 1 、 The sample characteristic data will be expressed as average, SD, and median, and the category variables will be displayed in the form of count and percentage.
- 2 、 The 95% confidence interval will show the original data and the change from the baseline.
- 3 、 The difference between the three groups was analyzed using one-way ANOVA to analyze the comparison between the intubation and non-intubation groups for drug administration, the presence or absence of complications, the severity and

the degree of completion of the operation.

- 4 ‧ The differences between the groups will be evaluated by chi-square test or Fisher's exact test.
- 5 ‧ Unless otherwise stated, all statistical tests will be two-way and evaluated at a significance level of 0.05.

Sample size calculation :

The main purpose of the study will focus on the completion of surgery and the occurrence of complications. In order to obtain the total number of participants in the study, a sample size will be calculated to detect a difference in incidence reduction of 25%. A statistical power of 80%, a 5% alpha and up to 10% possible sample loss. Therefore, each group will require 30 patients (90 in total). Considering the number of patients undergoing laryngoscope microsurgery each year, we estimate that there may be a total of 45 patients within a year. After meeting the inclusion criteria and obtaining patient consent, 45 patients will be included in the treatment plan in the first year, and the remaining sample size will be completed next year.

Primary outcome(2nd year) :

- 1 ‧ Less carbon dioxide retention and less hypercapnia.
- 2 ‧ Reduce postoperative lung complications.

Statistics from 10/20/2020 to 5/11/2021 :

Table I-i. Baseline demographics

Variable	G1(n=11)		G2(n=7)		G3(n=11)		p-value
	Mean	SD	Mean	SD	Mean	SD	
Age	52.0	13.9	46.9	8.4	51.7	14.2	0.66
BMI	26.4	5.5	24.5	3.5	25.1	2.5	0.78

Table I-ii. Baseline demographics

Variable	G1(n=11)		G2(n=7)		G3(n=11)		p-value
	n	(%)	n	(%)	n	(%)	
Sex							
male	7.0	63.6	3.0	42.9	5.0	45.5	0.60
female	4.0	36.4	4.0	57.1	6.0	54.5	
ASA							

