i:oxygen saturation 2: able to maintain oxygen saturation >92% on room air; 1: needed oxygen inhalation to maintain oxygen saturation >90%; 0: oxygen saturation <90% even with oxygen supplement ii:respiration 2: able to breathe deeply and cough freely; 1: dyspnea or limited breathing; 0: apneic iii:circulation 2: blood pressure ±20% of preanesthetic level; 1: blood pressure from ±20% to 49% of preanesthetic level; 0: blood pressure ±50% of preanesthetic level iv:consciousness 2: fully awake; 1: arousable on calling; 0: not responding v:activity 2: able to move 4 extremities voluntarily or on command; 1: able to move 2 extremities voluntarily or on command; 0: unable to move extremities voluntarily or on command						

Surgical records

	Ant.	Middle	Post.	Mixed	
Lesion site					
	Vocal polyp	Vocal cyst	Vocal atrophy	Vocal paralysis	Laryngeal tumor Bx
LMS Procedures					
Surgery completion	 Complete		 Partially complete		 Incomplete
Satisfaction	 Satisfied		 Partially satisfied		 Unsatisfied
Vision	 Good		 Poor		
Poor Visualization	 Inability to suppress gag reflex  Inability to achieve anesthesia  Had to change approach  Others:		 Copious secretions  Difficulty with vocal cord injection		
The Cormack-Lehane (CL) glottis view classification  I  IIa  IIb  III  IV					
					
Laryngeal compress :  Not applied  Applied					
Stress index  1  2  3  4  5					
Other :					

Postoperative evaluation

I. Evaluation (Score : none=1,minor=2,moderate=3,severe=4) , **time** :

- Sore throat : _____
- Hoarseness : _____
- Swallowing difficulty : _____
- Breathing difficulty : _____

II. Ward recording (24hr postoperative event) :

Score	Nausea()	Vomiting()	Nausea/vomiting()
0	none	none	none
1	minor	minor	minor
2	moderate	moderate	moderate
3	severe	severe	severe

D EXPECTED WORK ITEMS AND SPECIFIC RESULTS

Projects expected to be completed in the second year

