1. Improve the success rate of laryngoscopic microsurgery for patients with non-intubated anesthesia.
2. Provide excellent surgical field of vision and complete examination of vocal cords.
3. Bilateral superior laryngeal nerve block surgery replaces muscle relaxants to keep patients breathing spontaneously and avoid carbon dioxide retention and hypercapnia.

Contribution to clinical or academic

Non-intubation anesthesia laryngoscope microsurgery without muscle relaxants can be used for more patients who need laryngoscope microsurgery but have higher cardiovascular and cerebrovascular risks. Surgeons can use more operation time to reduce stress and complete the operation without interruption.

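### The protocol ranks pCO2 as secondary in one place and CO2 retention as primary in another, and does not say which result decides the single 90-patient comparison

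*Protocol*

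**What the plan says.** Four places in the protocol bear on what the trial is to decide.

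- **Section C, outcome paragraphs.** The surgeon's "score on the degree of surgical completion was taken as the primary outcome". The blood gases are taken to look at pCO2 "in different groups and as a secondary result".
- **Section C, list after the sample size calculation.** Under "Primary outcome(2nd year" stand two items: CO2 retention/hypercapnia, and postoperative lung complications.
- **Section C, Sample size calculation.** "The main purpose of the study will focus on the completion of surgery and the occurrence of complications". The 30 per group follow from a 25% reduction in incidence, 80% power, 5% alpha and 10% loss.
- **Abstract, Results.** The 30 per group are collected "to compare the effects of intubation and non-intubation on the surgical field of vision and the changes in blood oxygen during the operation". The word primary is not used here.

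The abstract counts 29 patients as collected and 61 as still needed, so the 29 belong to the 90. Results by group for the 29 (10/20/2020 to 5/11/2021) follow in Tables I to VIII.

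**The concern.** Completion, mean PaCO2 and lung complications are different variables and need different numbers of patients. With completion and CO2 each called primary somewhere, the trial could end with no difference in completion and a clear one in PaCO2, and either could be reported as its primary result.

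The timing adds to this. The document that carries the second-year list also shows that completion did not vary in the first 29 patients and that PaCO2 differed strongly. If CO2 became primary because of that difference, a test at 5% in a sample that still contains the 29 has a type I error above 5% and tends to overstate the effect. If CO2 was primary beforehand, no such inflation arises.

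**Working it through.** **1. The ranks side by side.** pCO2 is secondary in the outcome paragraphs, CO2 retention is primary in the second-year list, and PaCO2 has no part in the sample size. Completion is primary in the outcome paragraphs, part of the sizing basis, and absent from the second-year list. No sentence says that one list replaces the other or that the two years are separate comparisons.

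**2. What the 30 per group can be.** The baseline incidence is not stated. For 25% v 0%, two-sided 0.05, 80% power, mean proportion 0.125:

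n = [1.960 x sqrt(2 x 0.125 x 0.875) + 0.842 x sqrt(0.25 x 0.75)]^2 / 0.25^2 = (0.917 + 0.364)^2 / 0.0625 = 26.3, so 27; 27 / 0.9 = 30.

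Other baselines for a 25-point reduction need more (30% v 5%: 36, or 40 with loss; 50% v 25%: 58, or 65). So 30 can be reached only as a calculation for an incidence, not for mean PaCO2.

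**3. What had been seen in the 29.**
- Completion (Table VI): 11/11, 7/7, 11/11, marked as not suitable for statistics.
- Intra-operative PaCO2 (Table II), mean (SD): G1 54.4 (7.6), G2 86.4 (21.7), G3 55.5 (10.8), p = 0.00.
- Recomputed from these: between-group SS 5259.1 on 2 df, within-group SS 4569.3 on 26 df, F = 14.96, p = 0.00005.
- SE for G2 v G3 = sqrt(21.7^2/7 + 10.8^2/11) = 8.82; Table VIII prints 8.8281.

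**4. If the primary outcome was picked on those results.** Simulation under no true difference, with 11/7/11 patients first, 19/23/19 later, and K candidate outcomes. K is an assumption. The outcome picked on the first 29 is then tested at 5% in the pooled 90. Three-group ANOVA, equal SDs, independent outcomes:

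| Rule | K = 2 | K = 10 |
|---|---|---|
| smallest interim p decides | 7.1% | 13.9% |
| switch only if interim p < 0.05 | 5.7% | 10.6% |

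With correlation 0.5, or with a Welch test of G2 v G3 at the interim SDs, the results lie between 5.5% and 12.2%. In the 61 later patients alone the error is about 5% throughout.

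**5. If completion is kept.** Zero failures in 29: exact two-sided 95% upper bound = 1 - 0.025^(1/29) = 11.9%. The protocol plans three-group tests. At 30/30/30 with failures in one group only:
- Fisher: 3/0/0 gives p = 0.104, 4/0/0 gives p = 0.032.
- One-way ANOVA: 3/0/0 gives p = 0.045.

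None of the first 29 failed, so all failures must come from the 30 - 11 = 19 or 30 - 7 = 23 new patients of one group. Binomial chance, assuming none in the other groups:

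| Assumed failure rate | at least 4 of 19 / of 23 | at least 3 of 19 / of 23 |
|---|---|---|
| 10% | 11.5% / 19.3% | 29.5% / 40.8% |
| 20% | 54.5% / 70.3% | 76.3% / 86.7% |

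**6. If PaCO2 is chosen.** Welch power for G2 v G3, two-sided 0.05, SDs 21.7 and 10.8 (from 7 and 11 patients), at assumed differences of 10/12/15 mmHg:

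| Sample | No loss | 10% loss |
|---|---|---|
| all 90 | 30 v 30: 59.8/75.5/91.2% | 27 v 27: 55.2/70.8/88.0% |
| 61 later patients | 23 v 19: 46.9/61.8/80.6% | 21 v 17: 43.3/57.4/76.5% |

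At the interim difference of 30.9 mmHg, which may be too high, power without loss stays above 99% in both samples.

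**The case against.** A reader might infer that the sponsor switched the primary outcome to CO2 after seeing the interim difference. The document does not support that. Avoiding CO2 retention is part of the rationale in the abstract and in section B. It is also a stated hypothesis (Ho2: "Non-intubation and no muscle relaxation has less carbon dioxide retention and less hypercapnia"). Section D, under "Projects expected to be completed in the second year", lists the nerve block as a way "to keep patients breathing spontaneously and avoid carbon dioxide retention and hypercapnia". The items under the disputed heading read much like those deliverables, so the year label may mark only a project phase. This stands: a switch is a possibility, not a finding, and the 6-14% depends on an assumed number of candidates. It does not remove the conflict, because the heading still says primary and the blood-gas paragraph still says secondary.

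A reader might also infer that completion cannot show a difference at all. That goes too far. A pairwise Fisher test at 30 v 30 would need 6 failures v 0 (p = 0.024; 5 v 0 gives 0.052), but the planned three-group tests need only 4 or 3. Half of the sizing basis is complications, and these did vary (sore throat 3/0/4 in Table III).

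Two limits also stand. The abstract is weaker evidence than the rest, since it names a purpose and not a primary outcome, and its blood-oxygen wording covers the whole blood-gas panel. Lung complications are not defined: Table III gives p = 0.43 for difficulty breathing, which may or may not belong to them, so the selection worry concerns CO2 only.

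**Conclusion.** The plan is wrong as written and must be corrected: pCO2 is called secondary and CO2 retention primary, the 90 are sized on something else, and nothing settles which result decides. This rests on the text alone and needs no assumption. A separate SAP, not seen here, could add detail but would not remove the contradiction from the protocol.

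That CO2 was chosen after the look cannot be excluded and is not demonstrated. Only if it happened does the pooled test exceed 5%, by an amount that grows with the number of candidate outcomes. Completion remains testable but is weakly informative: with Fisher's test, about a 12-19% chance of significance at an assumed 10% failure rate in one group and 55-70% at 20%, with no failures elsewhere and no loss. The planned ANOVA is less demanding.

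**What to change.** 1. Name one primary outcome for the 90-patient comparison, with its variable, time point and group contrast.
2. Make the abstract, the outcome paragraphs, the second-year list and the sample-size paragraph agree with it. If the year label marks only project work, retitle that list.
3. State when and why the outcome was chosen, relative to the 29-patient results.
4. Give the basis of the 90 for it: assumed difference and SD for PaCO2, or expected failure rates in view of 0/29 for completion.
5. If CO2 is chosen and cannot be shown to have been primary before those results, protect the type I error. One way is a confirmatory two-sided 0.05 test in the 61 later patients (19/23/19), with the 29 and the pooled 90 reported as supportive. A stagewise combination test or another valid adjustment would also serve. If CO2 was primary beforehand, or an outcome not selected on those results is kept, this step is not needed.

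Items 1 to 4 cost wording only and, in themselves, no extra patients. Restricting the test to the 61 costs precision: without loss, the G2 v G3 PaCO2 difference detectable with 80% power rises from 12.7 to 14.9 mmHg, and power falls by about 11 to 14 percentage points at 10 to 15 mmHg. The fall is similar with the protocol's 10% loss, from a lower starting level.

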The second group: the group using muscle relaxants will first give a low dose of cisatracurium about 1.5-3mg, and after the effect of Propofol TCI loses consciousness, 0.6mg/kg Rocuronium or 0.1mg/kg Cisatracurium will be administered. When the patient stops breathing, Optiflow is adjusted to 50L/min and maintained until the end of the operation, the patient resumed spontaneous breathing. The patient's head will strengthen and ensure that the airway is stable, and the laryngeal

microscope will erect and reveal the location of the lesion to facilitate surgery. Low-dose muscle relaxant succinylcholine will be given continuously to maintain muscle relaxation until the end of the operation.

The third group: the group without the muscle relaxant will first touch the rear of the hyoid bone to the greater cornu about 0.5-1cm below the inner side of the greater hornu, that is, the internal branch of superior laryngeal n(chart I). Injection through the thyrohyoid membrane 1% Lidocaine 1-2ml for bilateral Superior laryngeal nerve block, and intravenous injection of Lidocaine 1-1.5mg/kg, Propofol TCI occurs.

(chart I)

The patient loses consciousness after setting up the laryngoscope, and 10% Lidocaine spray is used for intratracheal spray. After the effect is produced, the operation can be performed. Optiflow is adjusted to 50 L/min and maintain until the end of the operation.

After the operation, Propofol TCI and remifentanil TCI are stopped to wake up the patient, and Optiflow is adjusted to 15-20L/min. Patients who are given muscle relaxants will be given 1 mg of Atropine and 2.5 mg of neostigmine after spontaneous breathing is restored. After the patient resumes complete spontaneous breathing, Optiflow is stopped, the patient will be put on an oxygen mask, and transferred to a postanaesthesia care unit PACU for postoperative observation. After leaving the PACU, the patient will be transferred to the general ward to observe for one night.

Target-controlled infusion (TCI) injection of propofol will be set to Schneider model, Ce-targeted: 2.0-4.0 ug/ml, remifentanil 2–6 ng/ml. GE Entropy EasyFit Sensor was used to monitor intraoperative State Entropy (SE), Response Entropy (RE) and

Surgical plethysmographic index (SPI), and as a reference for adjusting TCI propofol and remifentanyl.

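### Postoperative lung complications are a listed second-year primary outcome with no event definition, no time window and no line on the case report form, and the protocol names conflicting primary outcomes

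*Protocol*

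**What the plan says.** - **Outcome list (Section C, after the sample size calculation).** Two second-year primary outcomes are given. The first concerns carbon dioxide retention and hypercapnia; the second is "Reduce postoperative lung complications".
- **Hypotheses (Section C).** "Ho4: Non-intubation and no muscle relaxation may lead to less postoperative pulmonary complications". The list is introduced as assumptions to be explored.
- **Earlier in Section C, after the blood gas schedule.** The surgeon's "score on the degree of surgical completion was taken as the primary outcome". The same part ranks the blood gas (pCO2) comparison between groups as secondary.
- **Sample size calculation (Section C).** "The main purpose of the study will focus on the completion of surgery and the occurrence of complications". The type of complication is not given.
- **Postoperative course (Section C).** "After leaving the PACU, the patient will be transferred to the general ward to observe for one night".
- **Case report form.** The postoperative evaluation has a symptom list, including "Breathing difficulty" graded 1 to 4 with a blank time field, and a section headed "Ward recording (24hr postoperative event)", whose only columns are nausea, vomiting and the two combined.
- **Results so far.** The abstract says all 29 patients finished with no complications. Table III shows one group 3 patient with difficulty breathing, which its note places in the recovery room.

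**The concern.** A primary outcome needs a list of qualifying events, a period over which they are counted, and a place to record them. Lung complications have none of the three here. Patients are observed on the ward overnight, but the form does not ask about lung events there. Any result would then rest on reading charts afterwards and deciding case by case what counts. Because few events are likely, one or two such decisions could determine the result.

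One decision has already been made without a written rule. The group 3 breathing difficulty was reported as discomfort and not as a complication. Group 3 is the arm that Ho4 expects to benefit, so the rule for the next such case should not be left open.

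The conflict over what is primary adds to this. A reader cannot tell whether the trial will be judged on surgical completion, carbon dioxide, lung complications, or some combination.

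**Working it through.** **1. What the form collects, set against the outcome.**

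| Respiratory item on the form | When | Linked to lung complications? |
|---|---|---|
| SpO2, respiratory rate | before induction and in recovery | no |
| Blood gas | before, end of operation, recovery room | no |
| PACU oxygen and respiration subscores (0–2) | recovery room | no |
| Breathing-difficulty grade (1–4) | time left blank | no |
| 24-hour ward record | ward | nausea and vomiting only |

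The form does hold respiratory data. They are early signs or symptoms, and the ward period has no respiratory entry.

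**2. Which outcome is primary.**

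| Outcome | Section C, after the blood gas schedule | Sample size text | Second-year list |
|---|---|---|---|
| Surgical completion | primary | main purpose | not listed |
| Carbon dioxide | secondary | not named | primary, item 1 |
| Lung complications | not named | at most within unspecified complications | primary, item 2 |

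Carbon dioxide moves directly from secondary to primary between two parts of the same section.

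**3. Does the stated sample size settle it?** The plan gives 30 per group from a 25% reduction in incidence, 80% power, 5% alpha (two-sided) and 10% loss, with no base rate. Assume 25% against 0%, so the mean proportion is 0.125, and use the pooled two-proportion formula:

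n = [1.96·√(2·0.125·0.875) + 0.8416·√(0.25·0.75)]² / 0.25² = (0.917 + 0.364)² / 0.0625 ≈ 26.3, so 27; then 27/0.9 = 30.

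By symmetry, 100% against 75% gives the same 30. The figure therefore fits an assumed complication rate of 25% falling to 0%, and equally an assumed completion rate of 100% against 75%. It does not show which outcome was meant.

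**4. The one case in doubt.** Table III gives 0/11, 0/7 and 1/11 for difficulty breathing in groups 1, 2 and 3. Exact (Clopper-Pearson) 95% limits for group 3:

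- Not counted, 0/11: upper limit 1 − 0.025^(1/11) = 28.5%.
- Counted, 1/11 = 9.1%: lower limit 1 − 0.975^(1/11) = 0.2%; the upper limit solves (1−p)¹¹ + 11p(1−p)¹⁰ = 0.025, giving 41.3%.

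Two-sided Fisher tests if it counts: against 0/11, p = 1.0; against 0/7, p = 1.0; against groups 1 and 2 pooled (0/18), p = 11/29 = 0.38. No comparison changes.

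Taking the abstract's 0/29 at face value, the pooled upper limit is 1 − 0.025^(1/29) = 11.9%, which is consistent with few events.

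**5. What can still be recorded prospectively.** 90 − 29 = 61, and 61/90 = 67.8%. By group, against the target of 30: 30 − 11 = 19, 30 − 7 = 23, 30 − 11 = 19.

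**The case against.** **The authors already classified the case.** This is correct. The abstract reports no complications in 29 patients, and Table III files the dyspnoea under discomfort. A reader might infer that the interim result is open or tilted towards group 3. The documents do not support that: a classification was made, and the alternative would change no comparison. What stands is that no written rule backs it or binds the next 61 patients.

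**Definitions belong in the SAP, which is not shown.** This is partly right. Rules deriving an event from SpO2 or PACU subscores could sit there. But an SAP cannot recover ward events that the form never asked for, and it does not remove conflicting statements from the protocol.

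**Ho4 is only exploratory.** This is fair, since the hypotheses are introduced as something to explore. Ho4 should not be read as a formal confirmatory test. The point rests on the primary outcome list.

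**The second-year label may mark a deliberate, staged outcome.** It may. Conversely, a reader might infer that the primary outcome was switched after the first data were seen. The document supports neither reading: it does not say when or why the label was added, and the completion-score statement stands unqualified.

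**Section D omits lung complications from the second-year work items.** It speaks only of helping to "keep patients breathing spontaneously and avoid carbon dioxide retention and hypercapnia". That section lists expected deliverables, so its silence contradicts nothing, and no weight is placed on it.

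**The form has a time field, and the dyspnoea was noted in the recovery room.** That shows when one case was noted, not a prescribed time for all patients.

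**Conclusion.** The point holds. A listed primary outcome has no event definition, no window and no systematic capture during the overnight ward stay, and the protocol contradicts itself on which outcome is primary. It should be corrected before enrolment continues.

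Its size lies in measurability. In group 3 the answer so far is 0/11 (0–28.5%) or 1/11 (0.2–41.3%), with no effect on any interim test. It would go too far to say that the trial collects no respiratory data, or that its interim findings are wrong.

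The conclusion assumes that the printed form is the one in use and that no other document directs staff to record lung events on the ward. Ward charts may hold such information, but nothing here makes its recording uniform.

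**What to change.** Before the remaining 61 patients are enrolled:

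1. State which respiratory events count as a lung complication and over what period, including whether a breathing-difficulty symptom alone counts.
2. Add one respiratory-event line (yes/no, type, time) to the existing 24-hour ward record.
3. Fix the time at which the breathing-difficulty grade is taken.

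If this is not wanted, remove lung complications from the primary outcomes.

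In either case, reconcile the two statements in Section C and the sample size text: say which outcome is primary, where carbon dioxide ranks, and whether the second-year label marks a change made after the first 29 patients' data were seen.

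**Cost.** A short definition, one form line and, if wanted, a review of 29 charts; no new visit or procedure. The real price is in numbers. The first 29 patients (11, 7 and 11) lack systematic ward capture, and the definition cannot be blind to them. A prospectively recorded comparison on this outcome therefore has about 19, 23 and 19 patients instead of 30 per group, before any loss. A chart-based classification of the first 29 can be shown alongside, flagged as retrospective, if the charts hold enough information.
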